Additionally, participants will be screened for characteristics that may endanger them if consuming alcohol. This includes past-month alcohol or other substance use disorders, past-month mood or anxiety disorders, suicidal ideation, excessive alcohol use (BAC >.30%) in past 30 days, serious medical conditions, regular use of prescription psychotropic or pain medication, history of negative reactions to alcohol, history of treatment for alcohol or substance use disorders, **pregnancy or nursing**. [name] and [name] will be responsible for follow-up assessment and referral of individuals expressing suicidal ideation or significant psychological distress. A clinically trained graduate student, supervised by [name], will immediately follow-up by telephone with participants indicating past-month alcohol or other substance use disorder, mood disorder, anxiety disorder, or suicidal ideation to assess their level of risk and refer them for care. Assessment of suicide risk, referral and follow-up of suicidal individuals, facilitation of inpatient placement for acutely suicidal individuals, and reporting requirements involved in threats of imminent harm to self are all part of [name] ordinary clinical duties as an attending clinician at the UW medical center and the inpatient and outpatient psychiatry clinics at UWMC, thus in the extremely unlikely event of a severe adverse psychological reaction, could facilitate inpatient admission. We have previously used these procedures in a variety of studies to ensure participant safety.

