All participants will be required to stay in the lab until their BrAC has dropped below 0.03%. After peak intoxication, BrAC readings will be taken every 30 minutes and participants will be provided with entertainment (e.g. Netflix, board games etc.), food and non-alcoholic drinks. Participants will be reminded they are paid for their time including the time it takes to reach a BrAC of 0.03% and will be provided a free ride home using a taxi or ride-share service (e.g. Uber or Lyft) to ensure safe transportation. Prior to their bar lab visit, participants will be informed they must stay in the lab until they reach a 0.03% BrAC and are told they will be in the lab for the full evening (as late as midnight) and should not make plans following their lab visit. A clinically trained graduate student, who has been trained in principles of motivational interviewing, will be present to speak with any resistant participants. Should a participant attempt to leave prior to reaching a BrAC of 0.03%, campus police will be contacted to either a) escort the participant back to the lab if they agree to stay or b) take other necessary action to ensure the participant's safety. Note that this situation is exceedingly rare—participants are paid for their time waiting in the lab, are well aware of this requirement prior to their participation, and are generally happy to remain. Nonetheless, procedures are in place to handle this situation if it should arise.

Timeline Follow Back assessments and alcohol use assessments reported during daily diary reports will estimate BAC using number of standard drinks consumed, time spent drinking, sex, age, and weight. If a participants estimated BAC exceeds .30%, the PI will be notified immediately. Participants who reported a BAC greater than .30% will be contacted by a clinically trained graduate student and informed of the risk of lethality at doses above .30%, and provided with appropriate referrals. Participants who report an excessive BAC greater than .30% in the past 30 days at screening will be ineligible for participation and will additionally receive these resources.

Finally, participants will be debriefed after the completion of the study to address the deception used during alcohol administration procedures. Some participants will be drinking with undergraduate confederates and not peers. The use of confederates to match important group characteristics of the

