A data and safety-monitoring plan is in place for all research conducted at the [name] Lab. All participants are encouraged to contact the Investigator and the UW IRB to report complaints or adverse events. Instructions for reporting adverse events and complaints, as well as for contacting the Investigators, are included in the consent documents and on all contact emails provided to participants through the course of the study. Screening surveys are designed to assess individuals who may be endangered by drinking alcohol. This includes past-month alcohol or other substance use disorders, past-month mood or anxiety disorders, suicidal ideation, excessive alcohol use (BAC>.30%), serious medical conditions, regular use of prescription psychotropic or pain medication, history of negative reactions to alcohol, history of treatment for alcohol or substance use disorders, **pregnancy or nursing**. [name] and [name] will be responsible for follow-up assessment and referral of individuals expressing suicidal ideation or significant psychological distress. [name] or another clinically trained graduate student under [name] supervision will immediately follow-up by telephone with participants indicating past-month alcohol or other substance use disorder, mood disorder, anxiety disorder, or suicidal ideation to assess their level of risk and refer them for care. Assessment of suicide risk, referral and follow-up of suicidal individuals, facilitation of inpatient placement for acutely suicidal individuals, and reporting requirements involved in threats of imminent harm to self are all part of [name] ordinary clinical duties as an attending clinician at the UW medical center and the inpatient and outpatient psychiatry clinics at UWMC, thus in the extremely unlikely event of a severe adverse psychological reaction, [name] could facilitate inpatient admission. We have previously used these procedures in a variety of studies to ensure participant safety. The PI or a clinically trained graduate student will be available during all alcohol administration runs to assess potential adverse events and will refer to proper resources when necessary. Further, Timeline Follow Back assessments and alcohol use assessments reported during daily diary reports will estimate BAC using number of standard drinks consumed, time spent drinking, sex, age, and weight. If a participants estimated BAC exceeds .30%, the PI will be notified immediately. Participants who reported a BAC greater than .30% will be contacted by a clinically trained graduate student and informed of the risk of lethality at BACs above .30%, and will be provided with appropriate referral resources. Participants who report .30% or greater BAC at screening will be ineligible for participation and will be followed up by phone to provide referrals. Any significant adverse events will be reported to the HSD within 48 hours, and all adverse events will be reported on the annual status report in compliance with federal regulations.

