a.1. Describe the clinically actionable results that are anticipated and explain which results, if any, could be urgent (i.e. because they pose life-threatening or severe health consequences if not treated or addressed quickly).

Examples of urgent results include very high calcium levels, highly elevated liver function test results, positive results for reportable STDs.

Individuals who meet clinical criteria will be contacted by phone to speak with a clinically trained graduate student or licensed clinical psychologist. If the individual met criteria for past month suicidal ideation, the clinician will do a full suicide risk assessment and create a plan with the individual to ensure their safety. They will also be provided with the national suicide prevention hotline and encouraged to call it at any time. The clinician will inform the participant the study is not right for them, and that they are at increased risk for the disorder(s) they met criteria for, and will explain this test is not diagnostic but simply suggests risk for mental health disorders. Clinicians will recommend they follow up with a mental health professional and will ask them to check their email for a list of local mental health resources, which includes free and insurance-accepting resources from UW and the surrounding community (see ‘CAPS mental health resources’ in supplementary materials). Clinicians will give the individuals opportunity to ask any questions before closing the call. Should someone not answer the phone, they will receive three phone calls with voicemails over a one week period and if no contact is made, this information and resources will be sent by encrypted email.

All eligible participants will also be provided the list of mental health resources. The following script will be used: “Throughout this study, you were asked many questions about your mental health. We are providing you with a list with many UW and local resources if you would like to continue to speak with someone about some of the topics brought up during this study or learn more about your mental health in general.”

The exact scripts used for these conversations will depend on several factors including 1) the presenting clinical problem 2) the level of expressed interest in mental health throughout the study and 3) the responses provided by the participant during the conversation.

a.2. Explain which of these results will be offered to subjects.

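### The no-answer rule in Protocol 10.10 (a.1) is the same for every positive screen, so an unreached person with past-month suicidal ideation may wait up to about a week for resources

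*Protocol*

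**What the plan says.** Section 10.10 (a.1) describes what happens to people who meet clinical criteria at screening. A graduate student with clinical training or a licensed psychologist telephones them.

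- **Reached, with suicidal ideation:** "If the individual met criteria for past month suicidal ideation, the clinician will do a full suicide risk assessment and create a plan". The national hotline number is also given.
- **Reached, any positive screen:** the clinician explains that the screen is not a diagnosis, recommends professional follow-up, and "will ask them to check their email for a list of local mental health resources".
- **Not reached, any positive screen:** "Should someone not answer the phone, they will receive three phone calls with voicemails over a one week period". If that fails, "this information and resources will be sent by encrypted email".

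The same section adds: "All eligible participants will also be provided the list of mental health resources".

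Sections 10.1 and 10.6 cover the first contact and who is responsible. A supervised caller "will immediately follow-up by telephone with participants indicating past-month alcohol or other substance use disorder, mood disorder, anxiety disorder, or suicidal ideation". Designated team members "will be responsible for follow-up assessment and referral of individuals expressing suicidal ideation or significant psychological distress".

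**The concern.** Suicidal ideation is the one screening result in this list for which a few days could matter a great deal. The plan recognises this during a completed call, where it adds a risk assessment, a safety plan and the hotline. It does not carry the distinction over to the missed call. There, ideation is treated like a positive screen for a substance use, mood or anxiety disorder, and the written fallback comes at the end of the call sequence.

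Two things are at stake. An unreached person gets the resource list, and perhaps the hotline number, later than necessary. In addition, the clinician who could decide on a different next step need not learn from the plan's own procedure that contact has failed.

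**Working it through.** This is a reading of procedure with one small timing calculation. The plan states no delay figure to reproduce.

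**Step 1: is there a faster or separate route elsewhere?**

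| Section | What it provides | Earlier route for an unreached person with suicidal ideation? |
|---|---|---|
| 4.6 | Data of ineligible screeners deleted once communication is complete | No |
| 8.2 (f) | Investigators' contact details on all materials | Only if the person makes contact |
| 10.1 and 10.6 | Immediate first call; designated follow-up clinicians | No; unanswered calls are not mentioned |
| 10.9 | Resources for people excluded for alcohol use, anxiety or mood disorder; a list for all at the end of participation | No; no timing is given and ideation is not named |
| 10.10 (a.1) | Three attempts, then email | No; one rule for all |
| 10.10 (a.3) and (d) | Scores withheld; results discussed by telephone | No |

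The rule in 10.10 (a.1) is therefore the only one that sets a time.

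**Step 2: how long is the wait?** Call the first unanswered call day 0. The email follows the third call. Spacing within the week is not stated, so the days below are assumptions.

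| Calls on days | Email on day | Days saved if sent on day 0 |
|---|---|---|
| 0, 1, 2 | 2 | 2 − 0 = 2 |
| 0, 2, 4 | 4 | 4 − 0 = 4 |
| 0, 3, 6 | 6 | 6 − 0 = 6 |
| Full week used | 7 | 7 − 0 = 7 |

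The resource list is delayed by 2 to 7 days. The hotline number is delayed by the same range, or by 0 days if the voicemails already give it.

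**Step 3: is the wait avoidable?** Section 4.1 collects the email address before the screening survey. Encrypted email is already the planned channel. The list goes to all eligible participants as well, so receiving it does not in itself reveal a result.

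**Step 4: how many people?** This cannot be estimated. The documents give neither the number screened nor the proportion who answer.

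**The case against.** The strongest reply is that the most important item, the hotline number, may not be delayed at all. Each attempt leaves a voicemail, and neither the voicemail content nor the call scripts are in the documents. That stands. What is certainly delayed is the general resource list.

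Second, calling first looks deliberate. Section 10.10 (a.3) doubts the validity of online self-report, and 10.10 (d) makes a telephone conversation the way to communicate results. An email about suicide sent only to flagged people would disclose the result before anyone had explained that the screen is not diagnostic. This also stands, and it determines how the email should be worded.

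Third, the case is already with a supervised, clinically trained caller, and nothing stops the responsible clinician from acting sooner. That is true, but nothing requires that clinician to be told that contact failed.

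Fourth, the criterion is past-month ideation, not identified acute risk. Such people are excluded under section 2.2, so no trial result is touched. The SAP reports a final sample of 13, so the change would mainly serve later use of the procedure. These points limit the gain but do not remove the delay.

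Two stronger readings should be resisted:

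- A reader might infer that the plan is silent on what happens after a missed call. It is not: 10.10 (a.1) gives further calls, voicemails and an email. The gap is only that these steps are not differentiated for suicidal ideation.
- A reader might infer that the plan handles very high estimated blood alcohol better, since section 10.1 says "If a participants estimated BAC exceeds .30%, the PI will be notified immediately". But that step comes before contact is attempted, and 10.1 gives no step for a high-alcohol participant who is not reached. It is no model for a no-answer rule.

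**Conclusion.** The point holds in a limited form. As written, the rule makes an unreached person with past-month suicidal ideation wait for the same call sequence as everyone else. The resource list is delayed by up to about 7 days, or about 2 if the calls fall on consecutive days. The hotline is delayed equally unless the voicemails give it. No section requires the designated clinician to be told that the person was not reached.

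This rests on assumed call spacing and on the absence of any separate route in the documents available; unseen scripts could narrow it. It concerns only people who miss every call. The gain is modest, the number affected is unknown, and eligibility, randomisation, endpoints and analysis are unchanged. It is a cheap improvement to participant safety and does not affect the trial's validity.

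**What to change.** In section 10.10 (a.1), after the no-answer sentence, add:

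> *If the person met criteria for past-month suicidal ideation, the CAPS mental health resources list, with the national suicide prevention hotline included and in neutral wording that does not state the screening result, will be sent by encrypted email on the day of the first unanswered call, and the clinician responsible for suicidal-ideation follow-up (10.1, 10.6) will be told the same day and decide the next step; the remaining calls continue.*

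The email, the list and the clinician role all exist in the plan already, so no new staff or materials are needed beyond the neutral wording. There are two costs: a little clinician time for each such case, which the documents do not allow one to price, and an email that arrives before the clinician's explanation, which the neutral wording limits. The sentence brings the resources forward and puts the decision with a responsible clinician. It does not guarantee that a risk assessment takes place. The voicemail script should be checked at the same time, to see whether it already gives the hotline number.

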11 ECONOMIC BURDEN TO PARTICIPANTS

11.1 Financial responsibility for research-related injuries. Answer this question only if the lead researcher is not a UW student, staff member, or faculty member whose primary paid appointment is at the UW.

For each institution involved in conducting the research: Describe who will be financially responsible for research-related injuries experienced by subjects, and any limitations. Describe the process (if any) by which participants may obtain treatment/compensation.

11.2 Costs to subjects. Describe any research-related costs for which subjects and/or their health insurance may be responsible (examples might include: CT scan required for research eligibility screening; co-pays; surgical costs when a subject is randomized to a specific procedure; cost of a device; travel and parking expenses that will not be reimbursed).

Travel expenses to the lab for alcohol administration procedures, if any are incurred, will not be reimbursed. Participants are encouraged to find a friend or family member to give them a ride.

Despite protections in place, some participants may become ill from consuming alcohol and may need medical attention. In this event, participants will be advised to be taken to UW Medical Center. However, participants who chose to go to an out of network (non-UW facility) provider may incur out of pocket expenses. Medical expenses incurred for out of network providers will be reimbursed up to \$10,000 through the Human Subjects Assistants Program.

12 RESOURCES

12.1 Faculty Advisor. (For researchers who are students, residents, fellows, or post-docs.) Provide the following information about the faculty advisor.

- Advisor's name
- Your relationship with your advisor (for example: graduate advisor; course instructor)
- Your plans for communication/consultation with your advisor about progress, problems, and changes.

12.2 UW Principal Investigator Qualifications. Upload a current or recent Curriculum Vitae (CV), Biosketch (as provided to federal funding agencies), or similar document to the Local Site Documents page in Zipline. The purpose of this is to address the PI's qualifications to conduct the proposed research (education, experience, training, certifications, etc.).

For help with creating a CV, see http://adai.uw.edu/grants/nsf_biosketch_template.pdf and <https://education.uwmedicine.org/student-affairs/career-advising/year-4/residency-applications/curriculum-vitae/>

The CV will be uploaded.

12.3 UW Study team qualifications. Describe the qualifications and/or training for each UW study team member to fulfill their role on the study and perform study procedures. (You may be asked about non-UW study team members during the review; they should not be described here.) You may list these individuals by name, however if you list an individual by name, you will need to modify this application if that individual is replaced. Alternatively, you can describe study roles and the qualifications and training the PI or study leadership will

require for any individual who might fill that role. The IRB will use this information to assess whether risks to subjects are minimized because study activities are being conducted by properly qualified and trained individuals.

Describe: The role (or name of person), the study activities they will perform, and the qualifications or training that are relevant to performing those study activities.

Examples:

Research Study Coordinator: Obtain consent, administer surveys, blood draw. Will have previous experience coordinating clinical research and be a certified phlebotomist in WA.

Undergraduate Research Assistant: Obtain consent, perform all study procedures. Will have had coursework in research methods, complete an orientation to human subjects protections given by the department, and will receive training from the PI or the graduate student project lead on obtaining consent and debriefing subjects.

Acupuncturist: Perform acupuncture procedures and administer surveys. Must be licensed with WA State DoH and complete training in administering research surveys given by the project director, an experienced survey researcher.

Co-Investigator: Supervise MRI and CT scan procedures and data interpretation, obtain consent. MD, specialty in interventional radiology and body imaging. 5-years clinical research experience.

Principle Investigator: Obtain consent, access participant contact info, supervise clinical calls, oversee study procedures, oversee data protections and sharing. Ph.D. in clinical psychology. Expertise in alcohol use research among college students. 20+ years clinical research experience.

Co-Investigator: Obtain consent, access participant contact info, oversee study procedures. Ph.D. Expertise in alcohol administration research. 20+ years research experience.

Clinical Graduate Student: Access participant contact info, conduct clinical calls. Clinical Psychology graduate student with motivational interviewing training. CITI and HIPAA training.

Supervisor: Obtain consent, access participant contact info, oversee bar lab procedures and emergencies, collect study data, debrief and pay participants. B.A. or B.S. in psychology or relevant field. CITI training.

Dedicated Scheduler: Access participant contact info, oversee screening procedures, contact participants via phone and email, collect data, schedule participants for bar lab run. Undergraduate or post-bac student in psychology or relevant field. CITI training

Undergraduate Research Assistant: Obtain consent, collect study data. Undergraduate or post-bac student in psychology or relevant field. CITI training.

12.4 Study team training and communication. Describe how it will be ensured that each study team member is adequately trained and informed about the research procedures and requirements (including any changes) as well as their research-related duties and functions.

There is no study team.

13 OTHER APPROVALS, PERMISSIONS, and REGULATORY ISSUES

13.1 Approvals and permissions. Identify any other approvals or permissions that will be obtained. For example: from a school, external site/organization, funding agency, employee union, UW Medicine clinical unit.

Do not attach the approvals and permissions unless requested by the IRB.

N/A

13.2 Financial Conflict of Interest. Does any UW member of the team have ownership or other Significant Financial Interest (SFI) with this research as defined by [UW policy GIM 10](#)?

No

Yes

→ If yes, has the Office of Research made a determination regarding this SFI as it pertains to the proposed research?

No

→ If no, contact the Office of Research [contact], [contact]) for guidance on how to obtain the determination

Yes

→ If yes, upload the Conflict Management Plan for every UW team member who has a FCOI with respect to the research, to **Zipline**. If it is not yet available, use the text box to describe whether the Significant Financial Interest has been disclosed already to the UW Office of Research and include the FIDS Disclosure ID if available.
